5.1.2 Exclusion criteria initial treatment

Patients are not eligible to be included in the trial only if any of the following criteria apply:

Medical conditions:

- 1. Patients must not be pregnant or breastfeeding.
- 2. Patients must not have history of uveal, acral, or mucosal melanoma.
- 3. Patients must have no ongoing or recent evidence (within the last 5 years) of significant autoimmune disease that required treatment with systemic immunosuppressive treatments which may pose a risk for irAEs.

 Note: Patients with autoimmune-related hyperthyroidism, autoimmune-related hypothyroidism who are in remission, or on a stable dose of thyroid-replacement hormone, vitiligo, or psoriasis may be included.
- 4. Patients must have no known primary immunodeficiencies, either cellular (e.g., DiGeorge syndrome, T cell-negative severe combined immunodeficiency [SCID]) or combined T and B cell immunodeficiencies (e.g., T and –B negative SCID, Wiskott Aldrich syndrome, ataxia telangiectasia, common variable immunodeficiency).
- 5. Patients with uncontrolled type 1 diabetes mellitus or with uncontrolled adrenal insufficiency are not eligible.

Clinical Trial Protocol BNT111-01

Page 51 of 133 Version: 7.0 Date: 09 FEB 2023

- 6. Patients must have no uncontrolled infection with human immunodeficiency virus, hepatitis B or hepatitis C infection; or diagnosis of immunodeficiency that is related to, or results in chronic infection. Mild cancer-related immunodeficiency (such as immunodeficiency treated with gamma globulin and without chronic or recurrent infection) is allowed.
 - a. Patients with known HIV who have controlled infection (undetectable viral load and CD4 count above 350 either spontaneously or on a stable anti-viral regimen) are permitted. For patients with controlled HIV infection, monitoring will be performed per local standards.
 - b. Patients with known hepatitis B virus (HBV) who have controlled infection (serum hepatitis B virus DNA PCR that is below the limit of detection AND receiving antiviral therapy for hepatitis B) are permitted. Patients with controlled infections must undergo periodic monitoring of HBV DNA per local standards. Patients must remain on anti-viral therapy for at least 6 months beyond the last dose of trial treatment.
 - c. Patients who are known hepatitis C virus (HCV) antibody positive who have controlled infection (undetectable HCV RNA by PCR either spontaneously or in response to a successful prior course of anti-HCV therapy) are permitted.
 - d. Patients with HIV or hepatitis must have their disease reviewed by the specialist (e.g., infectious disease specialist or hepatologist) managing this disease prior to commencing and throughout the duration of their participation in the trial.

Note: should be discussed with the medical monitor in case of uncertainties.

7. Patients with another primary malignancy that has not been in complete remission for at least 2 years, with the exception of those with a negligible risk of metastasis, progression or death (such as adequately treated carcinoma *in situ* of the cervix, basal or squamous cell skin cancer, localized prostate cancer, non-invasive, superficial bladder cancer or breast ductal carcinoma *in situ*).

Note: should be discussed with medical monitor in case of uncertainties.

Prior/concomitant therapy:

- 8. Current use or use within 3 months prior to trial enrollment of systemic immune suppression including:
 - use of chronic systemic steroid medication (up to 5 mg/day prednisolone equivalent is allowed); patients using physiological replacement doses of prednisone for adrenal or pituitary insufficiency are eligible,
 - b. other clinically relevant systemic immune suppression.
- 9. Treatment with other anti-cancer therapy including chemotherapy, radiotherapy, or investigational or biological cancer therapy within 3 wks prior to the first dose of trial treatment (6 wks for nitrosureas). Adjuvant hormonotherapy used for breast cancer in long-term remission is allowed (refer to exclusion criterion 7).

Page 52 of 133 Version: 7.0 Date: 09 FEB 2023

Other comorbidities:

- 10. Current evidence of ongoing NCI-CTCAE (v5.0) Grade > 1 toxicity of prior therapies before the start of treatment, with the exception of hair loss, hearing loss, Grade 2 peripheral neuropathy, or laboratory abnormalities not considered clinical significant per investigator's discretion, and those Grade 2 toxicities listed as permitted in other eligibility criteria.
- 11. Patients who have a local infection (e.g., cellulitis, abscess) or systemic infection (e.g., pneumonia, septicemia) which requires systemic antibiotic treatment within 2 wks prior to the first dose of trial treatment.
- 12. Patients who have had a splenectomy.
- 13. Patients who have had major surgery (e.g., requiring general anesthesia) within 4 wks before screening, have not fully recovered from surgery, or have a surgery planned during the time of trial participation.
- 14. Current evidence of new or growing brain or spinal metastases during screening. Patients with leptomeningeal disease are excluded. Patients with known brain or spinal metastases may be eligible if they:
 - had radiotherapy or another appropriate therapy for the brain or spinal bone metastases,
 - b. have no neurological symptoms that can be attributed to the current brain lesions,
 - c. have stable brain or spinal disease on the CT or MRI scan within 4 wks before randomization (confirmed by stable lesions on two scans at least 4 wks apart, the second scan can be carried out during screening),
 - d. do not require steroid therapy within 14 days before the first dose of trial treatment,
 - e. spinal bone metastases are allowed, unless imminent fracture or cord compression is anticipated.
- 15. History or current evidence of significant cardiovascular disease including, but not limited to:
 - angina pectoris requiring anti-anginal medication, uncontrolled cardiac arrhythmia(s), severe conduction abnormality, or clinically significant valvular disease,
 - b. QTc (F) prolongation > 480 ms,
 - c. arterial thrombosis or pulmonary embolism within ≤ 6 months before the start of treatment,
 - d. myocardial infarction within ≤ 6 months before the start of treatment,
 - e. pericarditis (any NCI-CTCAE grade), pericardial effusion (NCI-CTCAE Grade ≥ 2), non-malignant pleural effusion (NCI-CTCAE Grade ≥ 2) or malignant pleural effusion (NCI-CTCAE Grade ≥ 3) within ≤ 6 months before the start of treatment,
 - f. Grade ≥ 3 symptomatic congestive heart failure (CHF) or New York Heart Association (NYHA) criteria Class ≥ II within ≤ 6 months before the start of treatment.
- 16. Patients who have received a live vaccine within 28 days of planned start of trial therapy.

Page 53 of 133 Version: 7.0 Date: 09 FEB 2023

Other exclusions:

- 17. Known hypersensitivity to the active substances or to any of the excipients.
- 18. Presence of a severe concurrent illness or other condition (e.g., psychological, family, sociological, or geographical circumstances) that does not permit adequate follow-up and compliance with the protocol.
- 19. Prior treatment with BNT111 and/or with cemiplimab.

5.1.3 Inclusion criteria for entering add-on therapy

- 1. Patients must have confirmed disease progression on monotherapy in Arm 2 or 3 of the trial.
 - a. An initial radiological progression needs to be verified by BICR.
 - Radiological progression to be confirmed by two scans 4 to 12 wks apart unless initial progression is accompanied by new symptoms, or deterioration of PS not attributed to toxicity, in which case one scan is sufficient.
- 2. Patients must sign a new ICF to continue with add-on therapy. Informed consent must be documented before any add-on-specific procedure is performed.
- 3. WOCBP must have a negative serum (beta-hCG) at baseline. Patients that are post-menopausal or permanently sterilized can be considered as not having reproductive potential. For a definition of WOCBP, see Section 10.4.
- 4. Female patients of reproductive potential must agree to use adequate contraception during and for 6 months after the last trial drug administration (Section 10.4).
- 5. WOCBP must agree not to donate eggs (ova, oocytes) for the purposes of assisted reproduction during trial starting at screening, during the trial and for 6 months after receiving the last trial treatment.
- 6. A man who is sexually active with a WOCBP and has not had a vasectomy must agree to use a barrier method of birth control, e.g., either condom with spermicidal foam/gel/film/cream/suppository or partner with occlusive cap (diaphragm or cervical/vault caps) with spermicidal foam/gel/film/cream/suppository, and all men must also not donate sperm during the trial and for 6 months after receiving the last trial treatment. For a definition of adequate contraception, see Section 10.4.

5.1.4 Exclusion criteria for entering add-on therapy

- Prior toxicity related to trial medication should have resolved to NCI-CTCAE v5.0
 Grade ≤ 1 before the start of add-on treatment and may not have led to permanent discontinuation.
- 2. The time between confirmed PD on monotherapy and start of add-on therapy shall not exceed 6 wks.
- 3. Current evidence of new or growing brain or spinal metastases at baseline (lesions that remained stable during initial treatment are allowed).
- 4. Systemic immune suppression:

Page 54 of 133 Version: 7.0 Date: 09 FEB 2023

- a. use of chronic systemic steroid medication (up to 5 mg/day prednisolone equivalent is allowed); patients using physiological replacement doses of prednisone for adrenal or pituitary insufficiency are eligible,
- b. other clinically relevant systemic immune suppression.
- 5. Presence of cardiovascular, renal, hepatic or any other disease that in the investigator's opinion, may increase the risks associated with trial participation or require treatments that may interfere with the conduct of the trial or the interpretation of trial results.

5.2 Screen failures

Screen failures are defined as patients who consent to participate in the clinical trial but are not subsequently randomized. A minimal set of screen failure information is required to ensure transparent reporting of screen failure patients to meet the Consolidated Standards of Reporting Trials (CONSORT) publishing requirements and to respond to queries from regulatory authorities. Minimal information includes demography, screen failure details, eligibility criteria, and any serious AE (SAE).

Individuals who do not meet the criteria for participation in this trial (screen failure) may be rescreened once. Rescreened patients should be assigned a new patient number.

6 TRIAL TREATMENTS

Trial treatment is defined as any investigational treatments, or marketed products intended to be administered to a trial patient according to the trial protocol.

6.1 Trial treatments administered

In all countries participating in the trial, BNT111 and cemiplimab are considered as investigational medicinal products (IMPs). An overview of the trial treatments and dosage information is shown in Table 2.

Detailed information on how BNT111 and cemiplimab should be administered is described in the current Pharmacy Manual (Appendices 1 and 2).

Clinical Trial Protocol BNT111-01 Page 55 of 133 Version: 7.0 Date: 09 FEB 2023

Table 2: Trial treatments administered

IMP name	BNT111	Cemiplimab
Туре	Biologic	Biologic
Dosage form	Vial	Vial
Unit dose strengths	Each drug product CCI in a single-dose vial for dilution with 0.9% sodium chloride	Each vial contains CCI mg cemiplimab in 7 mL of solution
Dosage levels	and collapse total RNA for the first dose, and collapse total RNA subsequently per schedule in the SoAs. Lowest possible dose is collapse total RNA	CCI mg
Administration route	IV injection	IV infusion
Use	Experimental	Experimental
Sourcing	Provided centrally by the sponsor	Provided centrally by the sponsor
Packaging and labeling	IMP will be provided in a folding box. Each folding box and each vial will be labeled as per country requirement	IMP will be provided in a folding box. Each folding box and each vial will be labeled as per country requirement

Abbreviations: IMP = investigational medicinal product; IV = intravenous; RNA = ribonucleic acid; SoA = schedule of activities.

6.2 Schedule of trial treatments

Patients will receive BNT111 and cemiplimab as outlined in the respective SoA in Section 1.3.

Delayed doses of BNT111 are to be managed as following:

In patients receiving weekly BNT111 doses, if a given dose is delayed for >2 d outside the visit window this BNT111 dose is to be skipped, and the patient should receive the next planned BNT111 dose as per the respective SoA. Exception is to be made in cases where the first day of the subsequent treatment cycle is delayed (i.e., C2D1, C3D1, add-on C2D1, add-on C3D1). In such cases, the delayed dosing visit is not skipped but performed as soon as possible to minimize the delay of the second trial treatment administration (cemiplimab). This rule/exception is also applicable to a delay of the first day of the subsequent cycle treatment in Arm 2 patients (receiving BNT111 as monotherapy) and Arm 3 add-on treatment.

In patients receiving BNT111 as 3-weekly doses (from Cycles 3 or 4 onwards), if a given dose is delayed, the next trial treatment should be administered as soon as possible to minimize the delay of the second trial treatment administration (cemiplimab).

The schedule of BNT111 should be maintained throughout the treatment period, and when feasible, the investigator should try to harmonize with the administration of cemiplimab, especially if it is delayed at any time point.

Page 56 of 133 Version: 7.0 Date: 09 FEB 2023

Patients from Arm 2 who continue to add-on therapy should maintain the same dose of BNT111 as given during monotherapy treatment, if dose was reduced, this reduction should be maintained during combination therapy.

6.3 Duration of treatments

The duration of treatment with BNT111 + cemiplimab (Arm 1) or BNT111 or cemiplimab as single agents is up to 24 months and will continue until unacceptable toxicity, withdrawal of consent, discontinuation due to investigator's decision or (confirmed) disease progression. Treatment with cemiplimab and/or BNT111 may be continued through initial radiological disease progression if the patient derives clinical benefit, e.g., until symptomatic disease, confirmation of progression, or unacceptable toxicity (whatever comes first).

Patients in Arm 2 (BNT111 monotherapy) or Arm 3 (cemiplimab monotherapy) may enter add-on therapy (addition of the other compound). The start of the add-on therapy should be scheduled with as little therapy interruption as possible and at latest start within 6 wks after confirmed disease progression. The duration of therapy for patients entering into add-on therapy is a total of 24 months for both the monotherapy and add-on therapy part.

If one of the compounds needs to be discontinued, single-agent treatment with the other can continue upon investigator's and sponsor's agreement.

6.4 Preparation/handling/storage/accountability

The investigator or designee must confirm appropriate temperature conditions have been maintained during transit for all trial intervention received and any discrepancies are reported and resolved before use of the IMPs.

Only patients enrolled in the trial may receive trial treatment and only authorized trial site staff may supply or administer these treatments. All IMPs must be stored in a secure, environmentally controlled and monitored (manual or automated) area in accordance with the labeled storage conditions with access limited to the investigator and authorized trial site staff.

The investigator or designee, or the head of the trial site (where applicable) is responsible for IMP accountability, reconciliation, and record maintenance (i.e., receipt, reconciliation, and final disposition records).

Further guidance and information for trial treatment preparation and final disposition of unused IMP are provided in the Pharmacy Manual.

6.5 Measures to minimize bias: randomization and blinding

This is an open-label trial, potential bias in assigning patients to treatment groups will be reduced by automated randomization. Information on trial treatment will be inaccessible for the radiologists that assess the CT scans by central review (primary analysis, BICR).

Page 57 of 133 Version: 7.0 Date: 09 FEB 2023

6.6 Trial treatment compliance

Patients will receive trial treatment directly from the investigator or designee, under medical supervision. The date and time of each dose administered must be recorded in the source documents and recorded in the electronic case report form (eCRF). The dose of both trial treatments and trial patient identification will be confirmed by a member of the trial site staff other than the person administering the trial treatment.

6.7 Concomitant therapy

6.7.1 Permitted concomitant therapy

Any operation, treatment, medication or vaccine (including over-the-counter or prescription medicines, vitamins, and/or herbal supplements) or other specific categories of interest that the patient is receiving at the time of enrollment or receives during the trial must be recorded along with:

- Reason for use
- · Dates of administration including start and end dates
- Dosage information including dose and frequency

The medical monitor should be contacted if there are any questions regarding concomitant or prior therapy.

Investigators may prescribe concomitant medications or treatments deemed necessary to provide adequate supportive care except for those medications identified as "prohibited" (Section 6.7.2).

- Palliative radiotherapy during the trial will be allowed for local symptom control (e.g., pain) provided that:
 - (i) in the opinion of the investigator, the patient does not have PD AND
 - (ii) no more than 10% of the patient's bone marrow is irradiated AND
 - (iii) the radiation field does not encompass a target lesion.
- G-CSF and other hematopoietic growth factors may be used in the management of acute toxicity, such as febrile neutropenia, when clinically indicated or at the investigator's discretion.
- Blood cell transfusion or platelet transfusion is allowed during the trial if clinically indicated. No transfusion is allowed within 1 wk prior to trial treatment initiation.
- Steroid treatment is permitted to modulate symptoms of an irAE at the discretion
 of the investigator. Replacement therapy (e.g., thyroxine, insulin, or physiologic
 corticosteroid replacement therapy for adrenal or pituitary insufficiency) is
 permitted. However, whenever possible corticosteroid treatment (prednisone

Page 58 of 133 Version: 7.0 Date: 09 FEB 2023

> 5 mg daily orally [PO] or IV, or equivalent) should be avoided as it counteracts with the mechanism of action of the vaccine.

6.7.2 Prohibited concomitant therapy

The following concomitant therapies and medications are not allowed during the treatment phase:

- Any concomitant systemic anti-cancer therapy defined as any agent or combination of agents with clinically proven anti-neoplastic activity that achieves non-negligible systemic bioavailability after being administered by any route for affecting the malignancy, either directly or indirectly, including palliative and therapeutic objectives.
- Any immunosuppressive therapy including immunosuppressive or maintenance therapy with systemic corticosteroids (PO or IV prednisone > 5 mg per day, or its equivalent), unless required per investigator's decision for treatment of an AE (maintenance therapy of prednisone > 5 mg should be discussed with the medical monitor).

Note: Replacement therapy (e.g., physiologic corticosteroid replacement therapy for adrenal or pituitary insufficiency) is not considered a form of systemic treatment and is permitted.

- Immunization with live-attenuated vaccines 28 days prior to the first dose of BNT111 and 3 months after the last dose of BNT111.
- Concomitant treatment with interferon is prohibited for all patients included into the trial.

If a patient receives any of these during the trial, the sponsor must be notified for evaluation of whether the patient can continue treatment or not.

6.8 Dose modifications and interruptions

6.8.1 Interruption of the intravenous infusion of cemiplimab

The infusion of cemiplimab should be interrupted if any of the following AEs are observed:

- · sustained/severe cough
- rigors/chills
- rash, pruritus (itching)
- urticaria (hives, welts, wheals)
- diaphoresis (sweating)
- hypotension
- dyspnea (shortness of breath)

Page 59 of 133 Version: 7.0 Date: 09 FEB 2023

- vomiting
- flushing

The reaction(s) should be treated symptomatically. The restart of the infusion at an infusion rate of 50% on the same day is at the discretion of the investigator if the NCI-CTCAE grade of the AE is Grade \leq 1. For any AE with a NCI-CTCAE Grade \geq 2, no restart of the infusion on the same day is permitted yet continuation of trial therapy may be allowed depending of the evolution of the AE.

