(including, but not limited to, paraneoplastic encephalomyelitis, meningitis, myositis,	with clinical signs or symptoms of an immune-related adverse reaction not described elsewhere		ther immune-related adverse emains at Grade 0 to 1 after 5 mg/day prednisone or
solid organ transplant rejection, graft-vs-host disease, Guillain-Barré syndrome, central nervous system, inflammation, chronic inflammatory demyelinating polyradiculoneuropathy, encephalitis, myasthenia gravis, neuropathy peripheral, myocarditis, pericarditis, immune thrombocytopenic purpura, vasculitis, arthralgia, arthritis, muscular weakness, myalgia, polymyalgia rheumatica, Sjogren's syndrome, keratitis, stomatitis, thyroiditis ^b	 Grade 3 based on type of reaction or Grade 4 adverse reaction (excluding endocrinopathies) Grade 3 or 4 neurologic adverse reaction Grade 3 or 4 myocarditis or pericarditis Recurrent Grade 3 immune-related adverse reaction Persistent Grade 2 or 3 immune-related adverse reactions lasting 12 wks or longer (excluding endocrinopathies) Inability to reduce corticosteroid dose to 5 mg or less of prednisone or equivalent per day within 12 wks 	Permanently discontinue	Initial dose of 1 to 2 mg/kg/day prednisone or equivalent followed by a taper
Infusion-related reaction	Grade 1 or 2	Interrupt or slow rate of infusion	Initiate symptomatic
	Grade 3 or 4	Permanently discontinue	management

a. Toxicity should be graded with the current version of NCI-CTCAE.

Abbreviations: ALT = alanine aminotransferase; AST = aspartate aminotransferase; NCI-CTCAE = National Cancer Institute Common Terminology Criteria for Adverse Events; PD-1 = programmed cell death protein 1; PD-L1 = programmed death ligand 1; ULN = upper limit of normal.

b. Observed with cemiplimab or with other anti-PD-1/PD-L1 monoclonal antibodies.

Page 64 of 133 Version: 7.0 Date: 09 FEB 2023

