The key principles of these recommendations are to maintain the comfort of the patient by management of infusion-related AEs experienced by other patients through:

- Effective prophylaxis and management of nausea and vomiting to support the patient's hydration status.
- Rapid administration of an appropriate amount of fluids.
- Keep the patient warm.
- Maintain organ function such as blood pressure, cognitive function and urinary output.
- Close monitoring of cardiac and other organ function as guided by comorbidities.
- Clinical pictures may vary, and recommendations do not replace medical reason.
- Keep other causes for symptoms in mind.

Table 7: Recommendations for management of infusion-related reactions related to trial drug

NCI-CTCAE v5.0	Guidance
Grade 1 or 2	 Treat symptomatically as indicated, including antipyretics, antihistamines, and/or analgesics as needed.
	Treat fever and neutropenia if present.
	Monitor fluid balance; administer IV fluids as clinically indicated.
	Observe patients for at least 4 h.
	Continue next dose at the same dose level.
	 For subsequent dosing, consider to use pre-medication as prophylaxis as per local clinical practice. Corticosteroids should be avoided if possible as they may counteract the pharmacodynamic effects of BNT111.
Grade 3	Withhold further treatment with trial drugs that day.
	 Strongly consider cardiopulmonary and organ function monitoring in an Intensive Care Unit.
	• Closely monitor and maintain fluid balance; administer IV fluids as clinically indicated.
	Oxygen for hypoxia.
	Vasopressor support for hypotension refractory to IV fluids.

Clinical Trial Protocol BNT111-01

Page 69 of 133 Version: 7.0 Date: 09 FEB 2023

NCI-CTCAE v5.0 Guidance

- Other supportive care as clinically indicated (e.g., fever and neutropenia, infection).
- Consider administration of corticosteroids (e.g., methylprednisolone or dexamethasone), in addition to antihistamines, antipyretics.
- May receive the next dose of trial treatment if symptoms resolve to Grade ≤ 1 for three consecutive days with approval of the medical monitor.
- For subsequent dosing consider to resume treatment with reduced dose.
- For subsequent dosing, use pre-medication as prophylaxis as per local clinical practice. Corticosteroids should be avoided if possible as they may counteract the pharmacodynamic effects of BNT111 vaccine.

Grade 4

- · Cardiopulmonary and organ function monitoring in Intensive Care Unit.

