Immune-related skin adverse reactions, defined as requiring use of systemic corticosteroids with no clear alternate etiology, including severe cutaneous adverse reactions (SCARs), such as Stevens-Johnson syndrome (SJS) and toxic epidermal necrolysis (TEN) (some cases with fatal outcome), and other skin reactions such as rash, erythema multiforme, pemphigoid, have been reported in association with cemiplimab treatment (see locally approved label).

Patients should be monitored for evidence of suspected severe skin reactions and exclude other causes. Patients should be managed with cemiplimab treatment modifications and corticosteroids (see Table 3).

Cases of SJS, fatal TEN and stomatitis occurred following one dose of cemiplimab in patients with prior exposure to idelalisib, who were participating in a clinical trial evaluating cemiplimab in Non-Hodgkin Lymphoma (NHL), and who had recent exposure to sulfa containing antibiotics (see locally approved label). Patients should be managed with cemiplimab treatment modifications and corticosteroids as described above (see Table 3).

Immune-related nephritis

Immune-related nephritis, defined as requiring use of corticosteroids with no clear alternate etiology, has been observed in patients receiving cemiplimab (see locally approved label). Patients should be managed with cemiplimab treatment modifications and corticosteroids (see Table 3).

Other immune-related adverse reactions

Other fatal and life-threatening immune-related adverse reactions have been observed in patients receiving cemiplimab including paraneoplastic encephalomyelitis and meningitis (see locally approved label for other immune-related adverse reactions).

Patients should be monitored for signs and symptoms of immune-related adverse reactions and managed with cemiplimab treatment modifications and corticosteroids (see Table 3).

Infusion-related reactions

Cemiplimab can cause severe or life-threatening infusion-related reactions (see locally approved label). Patients should be monitored for signs and symptoms of infusion-related

Page 72 of 133 Version: 7.0 Date: 09 FEB 2023

reactions and managed with cemiplimab treatment modifications and corticosteroids. Cemiplimab should be interrupted or the rate of infusion slowed for mild or moderate infusion-related reactions. The infusion should be stopped and cemiplimab should be permanently discontinued for severe (Grade 3) or life-threatening (Grade 4) infusion-related reactions (see Table 3).

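### Protocol 6.8.1 contradicts Table 3 and Section 6.8.4.2 on cemiplimab infusion reactions of Grade 2 and above; separately, Table 7 leaves its drug scope unclear at Grade 3

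*Protocol*

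**What the plan says.** Three places in the Protocol tell a site what to do about a reaction to a cemiplimab infusion.

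- **Section 6.8.1** lists events, such as chills, urticaria, hypotension and dyspnea, for which the infusion should be interrupted. At Grade 1 or lower, "The restart of the infusion at an infusion rate of 50% on the same day is at the discretion of the investigator". For any event of Grade 2 or higher, "no restart of the infusion on the same day is permitted yet continuation of trial therapy may be allowed", subject to the course of the event. No upper grade is given.
- **Table 3 (Section 6.8.3)**, in its infusion-related reaction row, gives "Interrupt or slow rate of infusion" for Grade 1 or 2 and permanent discontinuation for Grade 3 or 4.
- **Section 6.8.4.2** repeats this in prose: "Cemiplimab should be interrupted or the rate of infusion slowed for mild or moderate infusion-related reactions", and the infusion is to be stopped and "cemiplimab should be permanently discontinued for severe (Grade 3) or life-threatening (Grade 4) infusion-related reactions".

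A fourth place is **Table 7**. It stands in Section 6.8.4.1, which is headed BNT111, but its title is "Recommendations for management of infusion-related reactions related to trial drug". For a Grade 3 reaction it withholds treatment that day and then adds: "May receive the next dose of trial treatment if symptoms resolve to Grade ≤ 1 for three consecutive days with approval of the medical monitor". At Grade 4 it stops the drug permanently.

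**The concern.** Section 6.8.1, Table 3 and Section 6.8.4.2 all govern cemiplimab, so the difference cannot be put down to different drugs. Two sites that see the same reaction can each follow the Protocol and act differently, including after a severe or life-threatening reaction.

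The data are exposed as well. Discontinuation of trial treatment because of a treatment-emergent adverse event is part of a secondary safety endpoint (Protocol Section 3). SAP 8.5.2 tabulates treatment-emergent events leading to interruption and to permanent discontinuation. If the action taken depends on which page a site reads, those counts partly measure site practice.

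**Working it through.** No arithmetic applies to the conflict itself. The check is to ask, grade by grade, whether an action that one text allows would breach another.

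| Grade | Action at the site | Section 6.8.1 | Table 3 and 6.8.4.2 |
|---|---|---|---|
| 2 | Interrupt, no restart that day | Complies | Complies |
| 2 | Slow the infusion and complete it | Breach | Complies |
| 2 | Interrupt, restart the same day | Breach | Not barred |
| 3 or 4 | Stop cemiplimab permanently | Complies (its clause is only permissive) | Complies |
| 3 or 4 | Stop that day, resume cemiplimab at a later visit after recovery | May be allowed | Breach |

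At each of Grades 2, 3 and 4 there is one action that satisfies every text, and at least one that a site could defend from one text while breaching another.

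**Can the Grade 3-4 clause be read away?** The words at issue in 6.8.1 are about continuing trial therapy, not cemiplimab by name. Sections 6.3 and 7.1.1 let one compound go on when the other is stopped, so in Arm 1 the clause could mean BNT111 alone. In Arm 3 before add-on, cemiplimab is the only trial therapy. There the clause can only mean more cemiplimab, and 6.8.1 is not limited by arm. This reading also leaves the Grade 2 difference untouched.

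**Does another section settle precedence?** Section 7.1.2 says cemiplimab may be fully dosed, withheld or permanently discontinued as set out in Section 6.8.3, which leads to Table 3. That indicates the governing section for discontinuation. It does not amend 6.8.1 or mention it, and it does not address slowing or same-day restart.

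**What does Table 7 add?**

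- For BNT111 only: it sits under the BNT111 heading, and cemiplimab has its own infusion-reaction paragraph in 6.8.4.2. Its Grade 3 option of resuming at a reduced dose is not open to cemiplimab (Section 7.1.2).
- For a wider scope: the title and the Grade 3 row speak of trial drug, trial drugs and trial treatment, and the subject is infusion reactions. Protocol Table 2 gives BNT111 as an injection and cemiplimab as an infusion, and Section 6.8.2 writes of injection-related reactions for BNT111.
- Effect by grade: at Grade 2 it is silent on slowing and restart; at Grade 4 it agrees with Table 3. Only at Grade 3 would it differ from Table 3 if applied to cemiplimab.

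The scope question can arise in practice. Cemiplimab may start 30 minutes after BNT111 (SOA1), and a reaction up to 60 minutes after a dose may count as infusion-related (6.8.4.1). In Arm 1 the BNT111 window can therefore run 60 − 30 = 30 minutes past the start of cemiplimab. When toxicity cannot be attributed, Section 6.8.2 says cemiplimab should be interrupted or discontinued, without saying which.

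**The case against.** The strongest reply has four parts.

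1. Section 6.8.1 is about interrupting an infusion on the day. Its last clause is permissive and conditional, so a site that stops cemiplimab at Grade 3 or 4 breaches nothing. This is true, but a site that resumes can cite the same clause. It still needs an upper grade limit or a cross-reference.
2. At Grade 2 the conflict is narrow, because interrupting without restart satisfies every text. This stands as a limit: the conflict lies in the option to slow and in the missing restart bar.
3. Section 6.8.3 presents Table 3 as recommended modifications alongside the local label, which is not available here. However, 6.8.4.2 separately states the permanent-discontinuation instruction, and a recommendation that departs from a stated prohibition still leaves sites with two instructions.
4. Table 7 belongs to BNT111. This is probably right. A reader might infer that 6.8.1, Table 3 with 6.8.4.2, and Table 7 all conflict at Grade 2 and at Grades 3-4. The documents do not support that: Table 7 leaves a scope ambiguity at Grade 3 and nothing more.

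A reader might also infer that the classification of adverse events of special interest becomes site-dependent. It does not. Protocol 8.4 and SAP 8.5.2 define these events by grade and relationship to cemiplimab, so a Grade 2 or higher infusion reaction related to cemiplimab qualifies however it is handled.

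**Conclusion.** The point holds: Section 6.8.1 is inconsistent with Table 3 and Section 6.8.4.2 at Grades 2, 3 and 4, and the text is wrong as written. Confidence is high for that mismatch. The point on Table 7 is lesser, a scope to be stated, and is relevant only at Grade 3.

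Those affected are cemiplimab recipients who have an infusion reaction of Grade 2 or higher. It is tempting to put the size at the 90 + 45 = 135 patients planned for Arms 1 and 3 (SAP Table 3.2), plus Arm 2 patients on add-on. That is the number exposed to cemiplimab, not the number who meet the conflicting text. The documents give no rate of such reactions for cemiplimab, so the number affected cannot be estimated.

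The consequence for analysis is that descriptive counts of events leading to interruption or discontinuation could vary with the site. Discontinuation for toxicity also appears in the SAP censoring table for PFS, DOR and DDC (Table 5.1), but any effect there cannot be sized. No effect on the primary ORR analysis is shown.

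The conclusion assumes that the events listed in 6.8.1 include infusion-related reactions as meant in Table 3, which the subject of both texts supports.

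**What to change.** Reconcile Section 6.8.1 with Table 3 and Section 6.8.4.2 so that one instruction per grade applies to cemiplimab. It should cover slowing and same-day restart at Grade 2, and whether the continuation clause in 6.8.1 extends to Grades 3 and 4. State in the title of Table 7 which drug it governs. The sponsor's clinical team must decide the content; this review takes no position on which rule is right.

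The cost is wording in the next protocol amendment and a clarification letter to sites. No change to the sample size or the statistical methods is needed.
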